#### Type of participant and disease characteristics

I 02. Participants with a physician diagnosis of COPD who meet the following criteria:

- Current or former smokers with a smoking history of  $\geq 10$  pack-years
- Moderate to severe COPD (post-bronchodilator  $FEV_1/FVC \leq 70\%$  and post-bronchodilator  $FEV_1$  % predicted  $>30\%$  and  $\leq 70\%$ ).
- Medical Research Council (MRC) Dyspnea Scale grade  $\geq 2$ .
- Patient-reported history of signs and symptoms of chronic bronchitis (chronic productive cough) for 3 months in the year up to screening in the absence of other known causes of chronic cough.
- Documented history of high exacerbation risk defined as exacerbation history of  $\geq 2$  moderate\* or  $\geq 1$  severe\*\* within the year prior to inclusion.

\*Moderate exacerbations are recorded by the investigator and defined as AECOPD that require either systemic corticosteroids (intramuscular (IM), intravenous, or oral) and/or antibiotics. One of the two required moderate exacerbations has to require the use of systemic corticosteroids.

\*\*Severe exacerbations are recorded by the investigator and defined as AECOPD requiring hospitalization / emergency room / urgent care visit.

- Background triple therapy (ICS+ LABA+ LAMA) for 3 months prior to randomization with a stable dose of medication for  $\geq 1$  month prior to Visit 1: (Double therapy: LABA + LAMA allowed if ICS is contraindicated)

I 03. Evidence of Type 2 inflammation: Patients with blood eosinophils  $\geq 300$  cells/microliter at Visit 1 (Screening).

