### 5.4 SCREEN FAILURES

Screen failures are defined as participants who consent to participate in the clinical study but are not subsequently randomly assigned to IMP. A minimal set of screen failure information is required to ensure transparent reporting of screen failure participants to meet the Consolidated Standards of Reporting Trials (CONSORT) publishing requirements and to respond to queries from regulatory authorities. Minimal information includes demography, screen failure details, eligibility criteria, and any serious adverse event (SAE).

Patients who are eligible for rescreening may be rescreened once for any reason. In the case of technical malfunction of equipment, the patient may be rescreened. Patients who fail the exclusion criteria may be rescreened during the open screening period of the study; a different patient identification number will be issued.

Retesting of eosinophil values is allowed up to three times during the screening period to meet inclusion criteria for showing eosinophil count ≥300 cells/microliter (I 03) before randomization. A patient who is unable to complete a successful spirometry effort as defined by ATS criteria can be retested one additional time during the screening period of the study.

There is no requirement for a waiting period between the screen-failure date and the rescreening date. The IVRS/IWRS report will flag rescreened patients. Patients that are rescreened must sign a new consent form and all Visit 1 procedures must be repeated.

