
Change in pre-bronchodilator FEV1 from baseline to Week 12
	
The change from baseline in pre-bronchodilator FEV1 at Week 12 will be analyzed using mixed-effect model with repeated measures (MMRM). The model will include change from baseline in FEV1 values up to Week 12 as response variables, and factors for treatment group, age, sex, baseline height, region (pooled country), asthma history (Yes or No), smoking status at screening (current smokers or not), visit, treatment-by-visit interaction, baseline pre-bronchodilator FEV1, and FEV1 baseline-by-visit interaction as covariates. An unstructured correlation matrix will be used to model the within-patient errors. Parameters will be estimated using restricted maximum likelihood method using the Newton-Raphson algorithm. The least square (LS) mean of the change in pre-bronchodilator FEV1 of each treatment group, difference in the LS mean changes between the dupilumab group and placebo, the corresponding 95% CI of the differences and p-values will be provided. For patients who discontinued the study treatment, off-treatment FEV1 values will be included in the analysis. Sensitivity analyses for handling missing data may include pattern mixture model by multiple imputation and tipping point analyses.
 
Subgroup analysis
 
To assess the consistency in treatment effects across different subgroup levels, subgroup analyses will be performed for the primary efficacy endpoints with respect to age, gender, region, race, weight, BMI, smoking status, disease severity (as % predicted post-bronchodilator FEV1), number of moderate-or-severe

Endpoint	Statistical Analysis Methods
	
COPD exacerbation events within one year prior to the study, pre- bronchodilator FEV1, and other factors that will be specified in SAP.
 
Baseline biomarker-by-treatment interaction on the efficacy endpoints will be analyzed to evaluate the potential predictive effect of baseline biomarkers on the treatment response.

Key secondary	
Change in pre-bronchodilator FEV 1 from baseline to Week 52	The change from baseline in pre-bronchodilator FEV 1 at Week 52 will be analyzed in a similar way as change from baseline in pre-bronchodilator FEV 1 at Week 12 and the model will include values up to Week 52 as response variables.

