- Number of severe COPD exacerbations experienced within one year before Visit 1
Among them, number of those required
 - systemic steroids and treatment days for systemic steroids
 - antibiotics and treatment days for antibiotics
 - emergency medical care visit only
 - hospitalization without ICU
 - hospitalization in ICU
- Number of treatment days with systemic steroids use for moderate or severe COPD exacerbations experienced within one year before Visit 1
- FeNO at baseline
- Eosinophil counts at baseline

Any technical details related to computation, dates, and imputations for missing dates are described in [Section 2.5](#).

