2.1.4.3 Laboratory safety variables

Clinical laboratory data consists of blood analysis, including hematology, clinical chemistry, and urinalysis including cotinine. Clinical laboratory values after conversion will be analyzed into standard international units and international units will be used in all listings and tables.

Blood samples for clinical laboratories will be taken at Visit 1(Week -4±1), Visit 2 (Week 0), Visit 4 (Week 4), Visit 5 (Week 8), Visit 6 (Week 12), Visit 9 (Week 24), Visit 12 (Week 36), Visit 16 (Week 52), Visit 19 (Week 64) and early termination unless otherwise specified. The laboratory parameters will be classified as follows:

- Hematology
 - **Red blood cells and platelets and coagulation:** hemoglobin, hematocrit, red blood cell count, platelet count
 - **White blood cells:** white blood cell count, differential count
- Clinical chemistry
 - **Metabolism:** glucose, total cholesterol, total protein, creatine phosphokinase
 - **Electrolytes:** sodium, potassium, chloride, bicarbonate
 - **Renal function:** creatinine, blood urea nitrogen, uric acid

- **Liver function:** alanine aminotransferase, aspartate aminotransferase, alkaline phosphatase, lactate dehydrogenase, total bilirubin (in case of values above the normal range, differentiation in conjugated and non-conjugated bilirubin), albumin
- **Pregnancy test:** Serum β -human chorionic gonadotropin (all female patients) will be performed at screening (V1) in women of childbearing potential, and a urine pregnancy test will be performed at V2 prior to randomization and every 4 weeks thereafter. A negative result must be obtained at V1 and V2 prior to randomization. In case of positive urinary test the study treatment will be withheld and a serum pregnancy test to confirm the pregnancy should be performed as soon as possible. Pregnancy will lead to definitive treatment discontinuation in all cases.

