2.1.6 Pharmacodynamic/genomics endpoints

Whole blood biomarkers blood eosinophil and neutrophil counts will be measured as part of the standard 5-part WBC differential cell count on a hematology auto analyzer.

For plasma/serum biomarkers, Eotaxin-3 will be assayed at Visit 2 (Week 0), Visit 4 (Week 4), Visit 6 (Week 12), Visit 9 (Week 24), Visit 16 (Week 52) and Visit 19 (Week 64); total IgE will be assayed at Visit 2 (Week 0), Visit 6 (Week 12), Visit 16 (Week 52) and Visit 19 (Week 64); Pulmonary and Activation-Regulated Chemokine [PARC] will be assayed at Visit 2 (Week 0), Visit 16 (Week 52) and Visit 19 (Week 64); Fibrinogen will be assayed at Visit 2 (Week 0), Visit 9 (Week 24), Visit 16 (Week 52) and Visit 19 (Week 64).

Fractional exhaled nitric oxide (FeNO; postbronchodilator) will be analyzed using a NIOX instrument (Aerocrine AB, Solna, Sweden), or similar analyzer using a flow rate of 50 mL/s, and reported in parts per billion (ppb). This assessment should be conducted prior to spirometry and following a fast of at least 1 hour at Visit 2 (Week 0), Visit 4 (Week 4), Visit 5 (Week 8), Visit 6 (Week 12), Visit 9 (Week 24), Visit 12 (Week 36), Visit 16 (Week 52) and Visit 19 (Week 64).

Pharmacogenetic testing is optional and voluntary. A separate written informed consent form must be signed before sampling. For those patients who signed the optional pharmacogenetic informed consent form, blood samples for exploratory genetic analysis of DNA or RNA will be collected at the study visit as specified in the study flow chart, and these samples will be stored for future analysis.

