For each of the above methods, a negative binomial model will be fitted using each of the complete datasets composed of observed and imputed data, including the total number of observed and imputed events during the 52 weeks as the response variable, with the treatment group, region (pooled country), ICS dose at baseline (high dose ICS [yes/no]), smoking status at screening (current smokers or not), baseline disease severity (as % predicted post-bronchodilator FEV1), and number of moderate or severe COPD exacerbation events within one year prior to the study (≤ 2 , 3, or ≥ 4) as covariates. Log transformed observation duration will be the offset variable for patients who complete the 52-Week treatment/study period, and log transformed 52 weeks will be the offset variable for patients who discontinue the study before Visit 16 (Week 52). SAS MIANALYZE procedure will be used to generate statistical

inferences by combining results from the analysis with each dataset using Rubin's formula.

More details of the imputation and analyses methods are provided in Appendix J:

Subgroup analyses

To assess the consistency in treatment effects across different subgroup levels, subgroup analyses will be conducted for the primary efficacy endpoint with respect to:

- Age group (<65, ≥65 years)
- Gender (Male, Female)
- Region
- Territory
- Race (Caucasian/White, Black/of African descent, Asian/Oriental, Others)
- Ethnicity (Hispanic or Latino, Not Hispanic or Latino)
- Baseline weight (<70, ≥70- < 90, ≥ 90 kg; <60, ≥ 60 kg)
- Baseline BMI (<25, ≥25- <30, ≥30 kg/m²)
- ICS high dose level at baseline (Yes, No)
- Smoking status at screening (current smokers, former smokers)
- Number of moderate-or-severe COPD exacerbation events within one year prior to V1 (≤2, 3, or ≥4)
- Number of severe COPD exacerbation events within one year prior to V1 (0, 1, ≥ 2)
- Baseline predicted post-bronchodilator FEV1% (<50%, ≥50%)
- Baseline pre-bronchodilator FEV1 (< median, ≥ median)
- Baseline FEV1 reversibility (<12%, ≥ 12%; < median, ≥ median)
- Baseline fractional exhaled nitric oxide (FeNO) (<20, ≥ 20 ppb)
- Baseline eotaxin-3 (< median, ≥ median)
- Baseline IgE (< 100 , ≥ 100 IU/ml)
- Baseline PARC (< median, ≥ median)
- Baseline Fibrinogen (< 350, ≥ 350 mg/dL)
- Baseline mMRC (< median, ≥median)
- Maximum eosinophils counts during screening (≥ 0.3-<0.5, ≥0.5 Giga/L)

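### Effect modification by eosinophils is tested only through the maximum screening count cut at 0.5 Giga/L, and the SAP specifies no continuous biomarker-by-treatment interaction

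*SAP*

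**What the plan says.** - **Subgroup factor.** SAP 2.4.4.1 lists "Maximum eosinophils counts during screening" as the only eosinophil factor; the fuller entry reads "Maximum eosinophils counts during screening (≥ 0.3-<0.5, ≥0.5 Giga/L". It enters a treatment-by-subgroup interaction in the negative binomial model, and SAP 2.4.4.2.1 reuses the list for FEV1 at Week 12.
- **Entry rule.** Protocol 5.1, criterion I 03, asks for "Evidence of Type 2 inflammation: Patients with blood eosinophils" of at least 300 cells/microliter at Visit 1. Protocol 5.4 adds: "Retesting of eosinophil values is allowed up to three times during the screening period to meet inclusion criteria".
- **A second pre-dose count.** SAP 2.1.4.3 states: "Blood samples for clinical laboratories will be taken at Visit 1(Week -4±1), Visit 2 (Week 0". SAP 2.1.6 states that "blood eosinophil and neutrophil counts will be measured as part of the standard 5-part WBC differential cell count". SAP 2.1.1 tabulates "Eosinophil counts at baseline" as a disease characteristic, but that value is not a subgroup factor.
- **Other biomarkers.** In the same SAP list, FeNO is cut at 20 ppb, IgE at 100 IU/ml, fibrinogen at 350 mg/dL, and eotaxin-3 and PARC at the median. All five use baseline values.
- **Protocol intention.** Table 9 of the protocol states, apart from the consistency subgroups: "Baseline biomarker-by-treatment interaction on the efficacy endpoints will be analyzed to evaluate the potential predictive effect of baseline biomarkers on the treatment response". It names no scale. SAP 2.4.6.2 gives biomarkers only descriptive statistics and plots. The list of changes to the protocol in SAP 1.5 does not mention the interaction analysis.

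**The concern.** The trial enrols on eosinophils and has an exploratory objective on biomarkers and treatment response. Whether benefit rises with the count above 300 is therefore a question it will be asked.

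The planned variable answers it poorly for two reasons. A patient who fails the cut-off can be tested again until a count passes, so the recorded maximum is partly true level and partly favourable measurement error. The value is then reduced to two classes. Both steps pull the estimated contrast between classes towards no difference, so a real gradient could look absent. If a continuous model is first chosen after unblinding, it will be post hoc.

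**Working it through.** **1. The plan's own figure.** The documents give no power for any eosinophil analysis. The stated figure is 90% power for the primary comparison (SAP 1.3: placebo rate 1.5, dabbled against 1.125 for dupilumab, dispersion 1, 0.95 year, 462 per arm, two-sided 0.049).

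V = [(1/(1.5×0.95) + 1) + (1/(1.125×0.95) + 1)]/462 = (1.7018 + 1.9357)/462 = 0.00787, so SE = 0.0887.

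Power = Φ(0.2877/0.0887 − 1.9685) = Φ(1.27) = 89.9%. This agrees with the plan.

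**2. Precision of a two-class interaction.** With a share p of patients in the upper class and the same rates and dispersion in both classes, SE = √(V/[p(1−p)]).
- p = 0.3: SE 0.194. The ratio of rate ratios detectable with 80% power at two-sided 0.05 is exp(−2.80×0.194) = 0.58.
- p = 0.5: SE 0.177, detectable ratio 0.61.

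So only a large difference between classes is detectable even if every patient is classified correctly.

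**3. Information kept by the planned variable.** If the effect is linear in the true log level, the information for the interaction is proportional to the squared correlation (R²) between the analysed variable and that level. I compared R² values by simulation: a Visit 1 count, retests only until a count reaches 0.3 (up to three), and one independent Visit 2 count.

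The grid is assumed, not taken from the documents: chance that a single count passes 20/30/40%; between-patient log SD 0.40/0.55/0.70; within-patient log SD 0.2/0.3/0.4/0.5. That makes 36 scenarios.

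The SAP can be read two ways. Its screening epoch (SAP 2.1.4) runs to just before the first dose, which would include Visit 2. Its study plan (SAP 1.4) places the screening period before randomization.

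| Planned split compared with | Visit 2 outside screening: loss | Visit 2 inside screening: loss |
|---|---|---|
| Continuous mean of all pre-dose counts | 39%–84% (median about 65%) | 37%–72% (median 52%) |
| Continuous Visit 2 count alone | 33%–76% | 29%–58% |

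Against the mean of all pre-dose counts, the loss exceeds half in 83% of scenarios with Visit 2 outside and 64% with it inside. The 0.5 cut alone, against the same count kept continuous, loses 30%–47% (median about 34%).

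**4. One scenario in detail.** Assume a screened-pool median of 0.2 Giga/L, between-patient SD 0.6, and within-patient SD 0.2/0.3/0.4.
- R² of the split with Visit 2 outside: 0.47/0.33/0.23. R² of the continuous mean of the qualifying and Visit 2 counts: 0.84/0.72/0.62. Loss: 44%/54%/62% (ratios taken before rounding).
- With Visit 2 inside, loss against all pre-dose counts: 39%/46%/53%.
- Patients classed at or above 0.5 whose true level is below 0.5: 32%/51%/66% with Visit 2 outside, 41%/57%/69% with it inside. Including Visit 2 recovers information but does not remove the upward selection.

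**5. If the true modifier is a step at 0.5.** With Visit 2 outside, the planned split keeps from 23% to about 100% of the information of the continuous mean, so the loss can vanish.

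**6. The other biomarkers.** For a normally distributed log value, a median split keeps 2/π = 64% of the information of a linear term. An interaction that the linear term would detect with 80% power then has power Φ(√0.637×2.80 − 1.96) = 61%. The 80% is illustrative. The result applies to eotaxin-3 and PARC only, because the other three use fixed cut-offs.

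**The case against.** The strongest points on the other side are these.

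- **Purpose.** These subgroups are there to check consistency. They are nominal, sit outside the testing hierarchy, and leave primary power and type I error alone. The counts are collected whatever the SAP says. This stands, and it makes the point an improvement rather than a threat to the trial's conclusion.
- **Protocol commitment.** A reader might infer that the SAP breaks a promise in Table 9. The documents do not support that: Table 9 does not say continuous, and the SAP does test treatment by biomarker class for exacerbations and Week 12 FEV1. What remains is that the protocol's aim of assessing prediction is served only by two-class splits.
- **First passing count.** A reader might infer that the maximum is simply the first count that qualified. That follows only if Visit 2 lies outside screening, which the SAP leaves open. In the simulation with up to three retests, the Visit 2 count exceeds the first passing count in 16%–38% of patients, so the two readings differ in practice.
- **Role of eosinophils.** They are the enrichment marker. The biomarker subgroup with tests in the hierarchy of SAP 2.4.4.3 is FeNO at or above 20 ppb, so calling eosinophils the main predictive biomarker would go beyond the text.
- **The existing classes.** They follow the entry criterion and place every eligible patient in one of two rows. A mean of pre-dose counts would still contain the selected count and would put some patients below 0.3. This is a fair reason to leave the forest-plot definition as it is.

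**Conclusion.** The point holds in a limited form. The SAP's only eosinophil interaction uses an upward-selected maximum cut in two, the five other biomarkers are likewise only dichotomised, and no continuous interaction is prespecified.

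The size is roughly 40% to 80% of the interaction information lost against a continuous mean of all pre-dose counts, with about a third due to the cut at 0.5. This rests on a log-linear effect and on assumed within-patient variability, between-patient spread and pass rate, none of which the documents give. A firm statement that more than half is lost is not supported: the milder scenarios lose less, and a true step at 0.5 could remove the loss. What is lost is precision in a prespecified exploratory analysis, not data.

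**What to change.** 1. State in SAP 2.4.4.1 whether the screening maximum includes the pre-dose Visit 2 count.
2. Prespecify a treatment by log(biomarker) interaction in the exacerbation model and the FEV1 models. For eosinophils use the baseline (Visit 2) count, which the entry rule does not select, or the mean of the pre-dose counts. For FeNO, IgE, eotaxin-3, PARC and fibrinogen use the baseline value. Add a check for non-linearity, such as a spline term, and a rule for zero values before taking logs.
3. Keep the existing splits for the forest plots.

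The cost is a short SAP addition and a few extra model fits on data already collected. The added results are nominal and exploratory and should be labelled so, since they increase the number of unadjusted interaction tests.

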2.4.4.2 Analyses of key secondary efficacy endpoints

2.4.4.2.1 Analysis of the change from baseline in pre-bronchodilator(pre-BD) FEV1 at Week 12 for dupilumab versus placebo

The change from baseline in pre-bronchodilator FEV1 at Week 12 will be analyzed using mixed-effect model with repeated measures (MMRM). The analysis will be performed in the full ITT population and also in the baseline FENO ≥ 20 ppb subgroup. The model will include change from baseline in FEV1 values up to Week 12 as response variables, and factors for treatment group, age, sex, height, region (pooled country), ICS dose at baseline (high dose ICS [yes/no]), smoking status at screening (current smokers or not), visit, treatment-by-visit interaction, baseline pre-bronchodilator FEV1, and FEV1 baseline-by-visit interaction as covariates. An unstructured correlation matrix will be used to model the within-patient errors. Parameters will be estimated using restricted maximum likelihood method using the Newton-Raphson algorithm. The least square (LS) mean of the change in pre-bronchodilator FEV1 of each treatment group, difference in the LS mean changes between the dupilumab group and placebo, the corresponding 95% CI of the differences and p-values will be provided. For patients who discontinued the study treatment, off-treatment FEV1 values will be included in the analysis.

Subgroup analyses

To assess the consistency treatment effects across the subgroup levels, subgroup analyses will be conducted for the change from baseline in pre-BD FEV1 at Week 12 with the same set of subgroups as defined for the annualized rate of moderate or severe AECOPD events in [Section 2.4.4.1](#).

Treatment-by-subgroup interaction at Week 12 and its p-value will be derived from a MMRM model. The model will include change from baseline in pre-BD FEV1 values up to Week 12 as response variables, and treatment, age, sex, height, region (pooled country), ICS dose at baseline (high dose ICS [yes/no]), smoking status at screening (current smokers or not), visit, treatment-by-visit interaction, baseline pre-bronchodilator FEV1, and FEV1 baseline-by-visit interaction, subgroup (if different than the aforementioned covariates), subgroup-by-treatment interaction and subgroup-by-treatment-by-visit interaction as covariates. If quantitative treatment by subgroup interaction at Week 12 is detected with nominal p-value < 0.05 for any subgroup factor, the Gail-Simon test will be used to test the qualitative interaction. Summary statistics of change from baseline in pre-bronchodilator FEV1 will be provided within each subgroup. Forest plot of LS mean difference and corresponding CIs for the subgroups will be provided.

Sensitivity analysis

Patients who discontinue the treatment are encouraged to follow the planned clinical visits, and all data collected after treatment discontinuation will be used in the analysis. Descriptive statistics of pre-BD FEV1 by visit up to Week 12 will be summarized for patients with some missing data and patients with complete data up to Week 12 separately. Number of patients with missing pre-BD FEV1, reasons and timing for missing pre-BD FEV1 will be summarized by treatment groups. In addition, following sensitivity analyses will be conducted to assess the robustness of the conclusion of the main model using the full ITT population:

Pattern mixture model-multiple imputation (PMM-MI)

Missing pre-BD FEV1 values will be imputed multiple times with adjustment for covariates including treatment groups, age, sex, height, region (pooled country), ICS dose at baseline (high dose ICS [yes/no]), smoking status at screening (current smokers or not), and baseline pre-BD FEV1. Each of the complete datasets will be analyzed using the ANCOVA model with change from baseline in pre-BD FEV1 at Week 12 as the response variable, treatment, age, sex, height, region (pooled country), baseline eosinophil strata, baseline ICS dose level, and baseline pre-BD FEV1 value as covariates. Then the SAS MIANALYZE procedure will be used to generate statistical inference by combining results using Rubin's formula.

Tipping point analysis

First, missing values will be imputed by PMM-MI as illustrated above. The imputed values in placebo group will then be shifted by adding a sequence of positive values and the imputed values in dupilumab group will be shifted by subtracting a sequence of positive values. For each combination of the shift parameters, each of the imputed and shifted datasets will be analyzed with the ANCOVA model and their results will be combined using Rubin's formula to generate statistical inference. LS mean difference between dupilumab and placebo in change from baseline in pre-BD FEV1 at week 12 and the corresponding p-values will be provided for each combination of shift parameters.

More details of the imputation and analyses methods are included in Appendix J.

2.4.4.2.2 *Analysis of the change from baseline in pre-bronchodilator FEV1 and SGRQ total score at Week 52 for dupilumab versus placebo*

The change from baseline in pre-bronchodilator FEV1 at Week 52 will be analyzed in a similar way as change from baseline in pre-bronchodilator FEV1 at Week 12 and the model will include values up to Week 52 as response variables. The analysis will be performed in the full ITT population and also in the baseline FENO \geq 20 ppb subgroup.

The change from baseline in SGRQ total score at Week 52 will be analyzed in a similar way as change in pre-bronchodilator FEV1 at Week 52 except that the MMRM model will include the following covariates: treatment group, region (pooled country), ICS dose at baseline (high dose ICS [yes/no]), smoking status at screening (current smokers or not), visit, treatment-by-visit interaction, baseline SGRQ total score, and SGRQ baseline-by-visit interaction.

Descriptive statistics including number of patients, mean, standard error, and least squares (LS) means will be provided. In addition, difference in LS means and the corresponding 95% confidence intervals (CI) will be provided along with the p-values.

2.4.4.2.3 *Analysis of proportion of patients with SGRQ improvement \geq 4 points at Week 52 dupilumab versus placebo*

The proportion of patients with SGRQ improvement \geq 4 points at Week 52 will be analyzed using a logistic regression model. The model will include treatment group, region (pooled country), ICS dose at baseline (high dose ICS [yes/no]), smoking status at screening (current smokers or not), and baseline SGRQ total score as covariates. For patients who discontinue treatment early, data collected during the off-treatment period will be used to determine the responder/non-responder status. Patients with missing SGRQ total score at Week 52 will be considered as non-responders.

Odds ratio of being a responder comparing dupilumab to placebo will be provided along with the corresponding 95% CI and p-value. Descriptive statistics including number and percentage of responders will also be provided.

Cumulative distribution function (CDF) of change from baseline in SGRQ at Week 52 will be presented by treatment group.

2.4.4.2.4 *Analysis of annualized rate of moderate or severe COPD exacerbation compared to placebo over the 52-week treatment period in the subgroup of patients with baseline FENO \geq 20 ppb*

The annualized rate of moderate or severe COPD exacerbation compared to placebo over the 52-week treatment period in the subgroup of patients with baseline FENO \geq 20 ppb will be performed in the same approach as that for the primary efficacy endpoint except that the analyzed population is not the full ITT population but the subgroup of patients with baseline FENO \geq 20 ppb.

The estimated annualized event rate for each treatment group and its two-sided 95% confidence intervals will be derived. The event rate ratio of the dupilumab group against placebo, its two-sided 95% confidence interval and p-value will be provided.

The rate difference between dupilumab and placebo, two-sided 95% confidence intervals of the rate difference and its p-value derived using delta method will also be provided as supportive information.

Mean cumulative function plot will be provided for descriptive purpose.

